4.4. Protocol Deviations

A listing will be provided of subjects in the safety analysis set who violated at least one inclusion or exclusion criteria. The listing will include the criteria not met and related comments.

5. BASELINE DATA

5.1. Demographics and Baseline Characteristics

Demographic summaries will include gender, race, ethnic origin, age, geographic region, and randomization age group (12–14 years, 15–17 years) and geographical location (European Union member states).

Study BL characteristic summaries will include body weight (kg), height (cm), BMI (kg/m²), and HBV genotype.

Descriptive statistics (sample size, mean, standard deviation, median, Q1, Q3, minimum, and maximum) will be summarized for continuous data and the number and percent of subjects will be summarized for categorical data.

Age is calculated as age in years at first dose of TDF and will be calculated using the following SAS code:

```
age2 = int(yrdif(birthdt, fdosedt, 'AGE'));
```

No inferential statistics will be computed. Data listings for demographics and BL characteristics will be provided using the Safety Analysis Set.

5.2. Baseline Disease Characteristics

Study BL disease characteristic summaries will include log₁₀ (HBV DNA [copies/mL]) level, HBV serology, ALT value ([U/L] including normal versus abnormal), AST value (U/L), number of years with HBV, number of years since first HBV treatment, spine and whole-body BMD ([g/cm²] via DXA scan), and serum bone biochemical markers (see Section 6.6).

Descriptive statistics (sample size, mean, standard deviation, median, Q1, Q3, minimum, and maximum) will be summarized for continuous data and the number and percent of subjects will be summarized for categorical data. Number of years with HBV and HBV treatment will be calculated from study BL.

5.3. Medical History

Disease-specific medical history will be collected on the CRF and will be summarized by monitoring group and overall by the number and percentage of subjects with each condition.

General medical history (i.e., conditions not specific to the disease being studied) data will be listed only. General medical history data will not be coded.

6. EFFICACY ANALYSES

6.1. Definition of the Primary Efficacy Endpoint

An efficacy analysis would be conducted after the last assigned subject completes Week 96 of TDF treatment for CHB. As the study has been prematurely discontinued, a descriptive analysis will be performed to outline the subjects who completed 96 weeks of treatment and review the HBV DNA results for subjects at their early discontinuation visit as part of study closeout proceedings.

The planned analysis will evaluate the difference in the proportion of subjects (Group 1 and 2 data will be analyzed separately and pooled as subjects have exposure to a single mode of therapy) achieving a composite endpoint of HBV DNA <400 copies/mL and ALT normal at Week 96, using a two-sided Fisher exact test with a non-completer equals excluded approach.

6.2. Statistical Hypothesis for the Primary Efficacy Endpoint

H₀: The difference between Monitoring Groups 1 and 2 in the proportions of subjects with HBV DNA <400 copies/mL at Week 96 is equal to 0

H₁: The difference between Monitoring Groups 1 and 2 in the proportions of subjects with HBV DNA <400 copies/mL at Week 96 is not equal to 0

6.3. Analysis of the Primary Efficacy Endpoint

The primary efficacy analysis will be conducted at the end of the study period, after the last randomized subject reaches Week 96, using the FAS. The analysis will evaluate the difference between monitoring groups in the proportion of subjects achieving the primary endpoint, using a Mantel-Haenszel test. As the study was prematurely discontinued, a descriptive analysis of subjects who met a composite endpoint of HBV DNA <400 copies/mL and ALT normal at Week 96 or at their early discontinuation visit will be reported.

6.4. Secondary Efficacy Endpoints

No secondary efficacy endpoints are planned.

6.5. Exploratory Efficacy Endpoints

PPD

6.6. Changes From Protocol-Specified Efficacy Analyses

None

7. SAFETY ANALYSES

7.1. Adverse Events and Deaths

7.1.1. Adverse Event Dictionary

Clinical and laboratory adverse events (AEs) will be coded using the Medical Dictionary for Regulatory Activities (MedDRA). System organ class (SOC), high level group term (HLGT), high level term (HLT), preferred term (PT), and lower level term (LLT) will be attached to the clinical database.

7.1.2. Adverse Event Severity

AEs are graded by the investigator as Grade 1 (mild), Grade 2 (moderate), Grade 3 (severe) or Grade 4 (life threatening) according to toxicity criteria specified in the study protocol. The severity grade of events for which the investigator did not record severity will be categorized as “missing” for tabular summaries and data listings, and will be considered the least severe for the purposes of sorting for data presentation.

7.1.3. Relationship of Adverse Events to TDF

Related AEs are those for which the investigator answers “Yes” to the question “Is there a reasonable possibility that the study treatment caused or contributed to the adverse event?” Events for which the investigator did not record relationship to TDF will be considered related to TDF. Data listings will show relationship as missing.

7.1.4. Serious Adverse Events

Serious adverse events (SAEs) are those identified as serious in the clinical database. The clinical database will be reconciled with the SAE database from the Drug Safety and Public Health Department before database finalization.

7.1.5. Treatment-Emergent Adverse Events

7.1.5.1. Definition of Treatment-Emergent

Treatment-emergent AEs are events in a given study period that meet one of the following criteria:

- Began on or after the date of the first dose of TDF and on or before the date of the last dose of TDF plus 30 days
- Had no recorded start date and the stop date is not before the first dose of TDF.

Exception: An event with an onset on the same or next calendar day that a previous event resolves is not treatment emergent if all of the following criteria are met:

- The events have the same MedDRA Lower Level Term
- The later event has the same or lower severity grade
- The later event is not related to TDF

7.1.5.2. Incomplete Dates

If the date of onset is incomplete, then the month and year (or year alone if month is not recorded) of onset determine treatment emergent as follows. The event is treatment emergent if the month and year of onset (or year of onset) of the event meets both of the following criteria:

- The same as or after the month and year (or year) of the first dose of TDF
- The same as or before the month and year (or year) of the 7th day after the last dose of TDF

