6.2. Pre-treatment Assessments

6.2.1. Screening Visit

Subjects will be screened within 30 days before assignment to determine eligibility for participation in the study. The following will be performed and documented at screening:

- 1) Obtain written informed consent
- 2) Obtain medical history
- 3) Complete physical examination including, vital signs, body weight, and height

- 4) Screen for pregnancy (serum screen) and contraceptive use
- 5) Conduct preliminary liver chemistry tests (ALT, ALP, AST, total and direct bilirubin, total protein, albumin, GGT, LDH, CK), serum renal chemistry (glucose, creatinine, creatinine clearance (calculated), magnesium, bicarbonate, chloride, potassium, sodium) and urinalysis (glucose, protein, creatinine, phosphate, bicarbonate, blood, calcium) (to be averaged with Baseline renal chemistry values), fasting required
- 6) HBV serology (HBeAg and HBsAg; anti-HBe and anti-HBs (if Ag negative))

Subjects meeting all of the inclusion criteria and none of the exclusion criteria will return to the clinic within 30 days after screening for commencement into the study.

From the time of obtaining informed consent through the first administration of Tenofovir DF, record all renal and bone AEs and any SAEs (not limited to bone or renal) on the adverse events case report form (CRF/eCRF). All other untoward medical occurrences observed during the screening period, including exacerbation or changes in medical history are to be captured on the medical history CRF/eCRF. See Section 7 Adverse Events and Toxicity Management for additional details.

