	
Estimated creatinine clearance using Schwartz Formula: $(\text{mL}/\text{min}/1.73\text{m}^2) = k \times L/\text{Scr}$ [k is a proportionality constant: for adolescent females ≥ 12 years old, $k = 0.55$, and for adolescent males ≥ 12 years, $k = 0.70$]; L is height in centimeters (cm); and Scr is serum creatinine (mg/dL)]
 
Parent or legal guardian of potential study subjects able to provide written informed consent prior to any screening evaluations and willing to comply with study requirements or subject able to provide written assent as determined by IEC/local requirements and at the Investigator's discretion.

Key Eligibility Criteria
	
Exclusion Criteria
 
Prior therapy with tTDF; subjects may have received prior interferon or oral anti-HBV nucleoside/nucleotide therapy (subjects experienced on interferon must have discontinued therapy for a minimum of six months; treatment-experienced subjects receiving oral anti-HBV nucleoside/ nucleotide treatment at screening should continue their current treatment regimen until tTDF is initiated (i.e., to prevent ALT flare)
 
Sexually-active males or females of reproductive potential who are not willing to use an effective method of contraception during the study.
 
Females who are pregnant or breastfeeding, or females who wish to become pregnant during the course of the study.
 
Known hypersensitivity to tTDF, the metabolites or formulation excipients
 
Any condition (including alcohol or substance abuse) or prior therapy that, in the opinion of the Investigator, would make the subject unsuitable for the study or unable to comply with treatment requirements

Study Periods/Phases
	
Screening period = 30 days
 
Total treatment period = 96 weeks

Randomization, Blinding, and Unblinding
	
 • 30 TDF-naïve subjects were randomized in a 1:1 ratio to receive tTDF 245mg PO daily and assigned to one of two safety monitoring groups (15 subjects each). • Randomization was not stratified by age or region. A centralized randomization procedure was used, whereby numbered bottles of TDF are assigned to subjects via an interactive voice response system (IVRS) according to the randomization code.

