7.1.6. Summaries of Adverse Events and Deaths

A brief summary of AEs will show, by monitoring group, the number and percentage of subjects who (1) had any treatment-emergent AE, (2) had any Grade 3 or 4 treatment-emergent AE, (3) had any Grade 2, 3 or 4 treatment-emergent AE, (4) had any treatment-emergent treatment-related AE, (5) had any Grade 3 or 4 treatment-emergent treatment-related AE, (6) had any Grade 2, 3 or 4 treatment-emergent treatment-related AE, (7) had any treatment-emergent SAE, (8) had any treatment-emergent treatment-related SAE, (9) permanently discontinued from TDF due to an AE, and (10) died during study.

Summaries (number and percentage of subjects) of adverse events (by SOC and PT) will be provided by monitoring group using the safety analysis set as follows:

- All treatment-emergent bone or renal AEs
- All TDF-related treatment-emergent bone or renal AEs
- Combined Grade 3 and 4 treatment-emergent bone or renal AEs
- Combined Grade 2, 3 and 4 treatment-emergent bone or renal AEs
- Combined Grade 3 and 4 treatment-emergent treatment-related bone or renal AEs
- Combined Grade 2, 3 and 4 treatment-emergent treatment-related bone or renal AEs
- All treatment-emergent serious AEs
- All treatment-emergent treatment-related SAEs

- All treatment-emergent AEs that caused permanent discontinuation from TDF
- All treatment-emergent AEs that caused change in dose or temporary interruption of TDF
- Deaths
- All AEs recorded between screening and first dose of TDF

For final analyses, summaries will be provided by monitoring group and overall TDF.

Summaries and data listings will use the Safety Analysis Set.

Events will be summarized based on the date of onset for the event, according to the definition of treatment emergent in Section 7.1.5. Non-treatment emergent events, including those prior to the first dose date of TDF, will be included in data listings.

Multiple events will be counted once only per subject in each summary. For data presentation, SOC will be ordered alphabetically, with PT sorted by decreasing total frequency. For summaries by severity grade, the most severe event will be selected.

In addition to the by-monitoring group summaries, data listings will be provided for the following:

- All AEs (with a variable indicating whether the event is treatment-emergent)
- SAEs (including deaths)
- AEs leading to discontinuation of TDF
- Subjects experiencing pregnancy during the study

PPD

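### SAP 7.1.5.2 ignores the stop date, so an AE known to have ended before first dose counts as treatment-emergent when its partial onset date falls in the first-dose month (or year, if the month is also missing)

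*SAP*

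**What the plan says.** SAP 7.1.5.1 gives the general definition, with a 30-day margin at the end of treatment. An event is treatment-emergent if it "Began on or after the date of the first dose of TDF and on or before the date of the last dose of TDF plus" that margin. A second route covers events that "Had no recorded start date and the stop date is not before the first dose of TDF". This second route is the only place in the treatment-emergent rules where the stop date is used.

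SAP 7.1.5.2 covers incomplete onset dates: "then the month and year (or year alone if month is not recorded) of onset determine treatment emergent as follows". Two criteria must both be met. The lower bound is "The same as or after the month and year (or year) of the first dose of TDF" and the upper bound is "The same as or before the month and year (or year) of the 7th day after the last dose of TDF". Both concern onset.

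The documents differ on which events are collected before dosing. Protocol 6.2.1 is broad: "From the time of obtaining informed consent through the first administration of Tenofovir DF, record all renal and bone AEs and any SAEs". Protocol 7.3 is narrower and asks, before drug initiation, for SAEs and for AEs related to protocol-mandated procedures. The SAP puts the window at "Screening period = 30 days" (1.2).

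SAP 7.1.6 sends non-treatment-emergent events, including pre-dose ones, to listings. It also plans a separate summary of "All AEs recorded between screening and first dose of TDF". Protocol 8.6.2 has no rule for partial dates.

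**The concern.** The two rules treat the same evidence differently. With no start date at all, a stop date before first dose settles the matter and the event is excluded. With a start month or year recorded, the event moves to 7.1.5.2, where the stop date plays no part. The fuller record can then be classified wrongly while the emptier one is classified correctly.

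Counting an event as treatment-emergent when its timing is unknown is an ordinary conservative convention. Here the relevant timing is known: the event ended before any drug was taken.

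Bone, renal and serious events are the focus of the safety tables. A misclassified event would enter the treatment-emergent counts. It would enter the TDF-related counts too if its relationship field were blank, because SAP 7.1.3 treats a missing relationship as related. It could also appear in the separate summary of events before first dose, and so be reported both ways.

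**Working it through.** The plan states no figure on this point to reproduce. The check has three parts.

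**1. Rule applied literally.** Illustrative first dose 20 March 2016, last dose 671 days later. The amended rule adds that the stop date, if known, is not before first dose.

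| Recorded onset | Stop | 7.1.5.2 as written | With stop-date criterion |
|---|---|---|---|
| March 2016, day missing | 10 March 2016 | treatment-emergent | not |
| 2016, day and month missing | 10 March 2016 | treatment-emergent | not |
| February 2016, day missing | 10 March 2016 | not | not |
| March 2016, day missing | 25 March 2016 | treatment-emergent | treatment-emergent |
| March 2016, day missing | ongoing | treatment-emergent | treatment-emergent |

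The first two rows are the defect. If their start date were wholly blank, 7.1.5.1 would exclude both. The third row shows that an earlier onset month is already handled correctly.

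**2. Share of resolved pre-dose events affected.** Assumptions, not in the documents: first-dose dates spread evenly over the calendar, onset within the 30 days before dosing, and every onset/stop pair before dosing equally likely.

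An onset *a* days before dosing (*a* = 1 to 30) allows *a* possible stop days before first dose. That gives 1 + 2 + … + 30 = 465 pairs per first-dose date. If first dose is on day *d* of its month, onset is in the same month only when *a* ≤ *d* − 1, which is *d*(*d* − 1)/2 pairs. Summed over a month, this is 4,960 pairs for 31 days, 4,495 for 30 days and 4,060 for 29 days.

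- Total pairs in 2016: 366 × 465 = 170,190.
- Month-only onset: (7 × 4,960 + 4 × 4,495 + 4,060) / 170,190 = 56,760 / 170,190 = 33.4%.
- Year-only onset: only January first doses can have an onset in the previous year. Those pairs number 31 × 465 − 4,960 = 9,455, so the share is 1 − 9,455 / 170,190 = 94.4%.

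Over 900 consecutive first-dose dates from July 2015 the shares are 32.9% and 95.5%.

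For a fixed duration of *L* days, the event resolves before dosing only if *a* > *L*. Over the same 900 dates, the month-only share is 44% for *L* = 3, 37% for *L* = 7 and 26% for *L* = 14.

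**3. Weight of one subject.** SAP 1.4 gives 30 enrolled, 15 per group: 1/30 = 3.3 percentage points overall and 1/15 = 6.7 in a group.

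**The case against.** The strongest reply is that the case is rare and does little harm. A misclassified record must arise in a 30-day window among 30 subjects, lack its onset day, have ended before dosing, and share its month (or year) with first dose. Several provisions work against this:

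- The protocol requires AE start and end dates in source (3.6, 8.12.5) and queries on data discrepancies (8.12.6).
- SAEs must be reported within 24 hours (7.3) and are reconciled with the safety database (SAP 7.1.4).
- Events with onset before consent and unrelated to a procedure go to medical history (Protocol 7.1.1).
- If Protocol 7.3 governs rather than 6.2.1, ordinary non-serious bone and renal events before dosing are not reported at all.

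Protocol 8.9 expects 4 to 5 renal or bone drug reactions in 100 subjects over 96 weeks. Scaled to 30 subjects and 30 days, that is 4.5 × 0.30 × 30/672 = 0.06 events. It is an on-treatment drug-reaction figure and only a loose guide to pre-dose events of any cause. The final analysis is descriptive, the AE listing carries a treatment-emergent flag, and the error over-counts events on drug, so it cannot hide a TDF signal.

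All of this stands and limits the importance of the point. None of it supplies the missing criterion.

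Three stronger readings are tempting but not supported:

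- *A missing onset day alone causes the error.* It does not; an earlier onset month is excluded.
- *About half of such events are affected.* Some 49% of all 30 pre-dose days share the first-dose month, but an event that also ended before dosing must have started earlier, which lowers the share.
- *Such records will certainly occur.* The documents give no count of partial dates and conflict on what is collected before dosing.

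**Conclusion.** The gap is real on the text: 7.1.5.2 has no stop-date check, 7.1.5.1 confines its check to events without a start date, and nothing else in either document closes the gap. It applies only to AEs with a partial onset date, a stop date before first dose, and an onset in the first-dose month, or year if the month is missing.

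Among resolved pre-dose events, roughly a quarter to under a half of those with month-only onset and about 95% of those with year-only onset would be misclassified. These shares depend on the assumptions about even first-dose dates, the 30-day window and event duration. They are proportions of a set whose size is unknown and probably very small, so no number of affected events can be claimed. With 15 subjects per group a single case would be visible in a table. The point is minor and worth correcting because it costs almost nothing.

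**What to change.** Add a third required criterion to SAP 7.1.5.2:

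> and the stop date, if known, is not before the date of the first dose of TDF (for a partial stop date, its month and year, or year, are not before those of the first dose)

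This aligns 7.1.5.2 with the stop-date logic of 7.1.5.1. It changes the status of no event that is ongoing or that stopped on or after first dose. The cost is one line of SAP text and one line of code. If tables have already been run, compare stop dates with first-dose dates in the bone/renal and serious AE listings (15.1 and 15.2).

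One separate matter in the same section can be settled in the same edit: the upper bound for partial dates uses the 7th day after last dose, whereas 7.1.5.1 uses last dose plus 30 days. The two should be reconciled.

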7.2.2. Assessment of Severity

Severity should be recorded and graded according to the GSI Grading Scale for Severity of Adverse Events and Laboratory Abnormalities ([Appendix 4](#)). For AEs associated with laboratory abnormalities, the event should be graded on the basis of the clinical severity in the context of the underlying conditions; this may or may not be in agreement with the grading of the laboratory abnormality.

7.3. Investigator Requirements and Instructions for Reporting Adverse Events and Serious Adverse Events to Gilead

Requirements for collection prior to Tenofovir DF initiation:

After informed consent, but prior to initiation of Tenofovir DF, the following types of events should be reported on the case report form (CRF/eCRF): all SAEs and AEs related to protocol-mandated procedures.

Adverse Events

Following initiation of Tenofovir DF, collect all bone and renal AEs, regardless of cause or relationship, until 30 days after last administration of Tenofovir DF must be reported to the CRF/eCRF database as instructed.

All bone and renal AEs should be followed up until resolution or until the adverse event is stable, if possible. Gilead Sciences may request that certain AEs be followed beyond the protocol defined follow up period.

Serious Adverse Events

All bone and renal SAEs, regardless of cause or relationship, that occurs after the subject first consents to participate in the study (i.e., signing the informed consent) and throughout the duration of the study, including the protocol-required post treatment follow-up period, must be reported to the CRF/eCRF database and Gilead Drug Safety and Public Health (DSPH) as instructed. This also includes any bone and renal SAEs resulting from protocol-associated procedures performed after informed consent is signed.

Any SAEs and deaths that occur after the post treatment follow-up visit but within 30-days of the last dose of Tenofovir DF, regardless of causality, should also be reported.

Investigators are not obligated to actively seek bone and renal SAEs after the protocol defined follow up period, however, if the investigator learns of any SAEs that occur after study participation has concluded and the event is deemed relevant to the use of Tenofovir DF, he/she should promptly document and report the event to Gilead DSPH.

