8.6.2. Adverse Events

Clinical and laboratory AEs will be coded using the Medical Dictionary for Regulatory Activities (MedDRA). System Organ Class (SOC), High-Level Group Term (HLGT), High-Level Term (HLT), Preferred Term (PT), and Lower-Level Term (LLT) will be attached to the clinical database.

Events will be summarized on the basis of the date of onset for the event. A treatment-emergent adverse event will be defined as any adverse event that begins on or after the date of first dose up to the date of last dose of Tenofovir DF plus 30 days.

Summaries (number and percentage of subjects) of treatment-emergent AEs related to **bone or renal SOCs** (hierarchically ordered by SOC, HLT, and PT) will be provided by treatment group:

- all treatment-emergent bone or renal AEs,
- all related treatment-emergent bone or renal AEs,
- combined Grade 2, 3, and 4 treatment-emergent bone or renal AEs,
- combined Grade 3 and 4 treatment-emergent bone or renal AEs,
- combined Grade 2, 3, and 4 related treatment-emergent bone or renal AEs,
- combined Grade 3 and 4 related treatment-emergent bone or renal AEs,
- all AEs that caused permanent discontinuation from Tenofovir DF,
- all AEs that caused permanent discontinuation from study,
- all AEs that caused change in dose or temporary interruption of Tenofovir DF,
- all serious AEs (all SOCs, i.e., not limited to bone or renal SOCs), and
- all serious bone or renal related AEs.

Events will be summarized based on the date of onset for the event. A treatment-emergent adverse event will be defined as any adverse event that begins on or after the date of first dose of Tenofovir DF. Events that occur prior to the first dose of Tenofovir DF or after the last dose of Tenofovir DF will be included in data listings.

PPD

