2. TYPE OF PLANNED ANALYSIS

2.1. Final Analysis

Final Analysis includes the time period from the first date of OL TDF dose through and including the date of last OL TDF dose plus 30 days. As a result of early study termination (FPFV July 2015 to LPLV April 2018) only two patients completed 96 weeks of observation on TDF treatment for HBV, the primary study objective to characterize the safety profile (renal and bone adverse outcomes) of subjects will be summarized based on available TDF exposure time. The assessment of efficacy and tolerability of TDF will be described. As most of the enrolled subjects were unable to complete the target observation period of 96 weeks, the final analysis will be unable to provide meaningful evidence to suggest whether enhanced or standard of care renal and bone monitoring frequencies between Group 1 and Group 2 offer early detection and mitigation of renal or bone adverse events. Instead, the data will be described by monitoring group and pooled together where possible.

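### SAP 7.1.5.2 tests adverse events with partial onset dates against day 7 after last dose, although 7.1.5.1 sets the treatment-emergent window at 30 days

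*SAP*

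**What the plan says.** **Complete onset date.** SAP 7.1.5.1 counts an event that began on or after first dose and "on or before the date of the last dose of TDF plus 30 days".

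**No onset date.** The same section also counts an event that "Had no recorded start date and the stop date is not before the first dose of TDF". This has no upper limit.

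**Partial onset date.** SAP 7.1.5.2 says that "the month and year (or year alone if month is not recorded) of onset determine treatment emergent". The month (or year) must be no earlier than that of first dose, and it must also be "The same as or before the month and year (or year) of the 7th day after the last dose of TDF".

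**Surrounding windows.** The SAP 2.1 analysis period runs "from the first date of OL TDF dose through and including the date of last OL TDF dose plus 30 days". SAP 7.2.2.1 and 7.2.2.2 (laboratory abnormalities) and 7.6 (concomitant medications) also use 30 days. Protocol 7.3 collects bone and renal AEs "until 30 days after last administration of Tenofovir DF". Protocol 8.6.2 first defines a treatment-emergent event as one that "begins on or after the date of first dose up to the date of last dose of Tenofovir DF plus 30 days". The only other 7-day limit is in SAP 7.2. It governs which laboratory values of early discontinuers are tabulated, not AEs.

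**Use.** SAP 7.1.6 builds the AE summaries on Section 7.1.5 and sends non-treatment-emergent events to listings.

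**The concern.** Section 7.1.5.2 should only apply the 7.1.5.1 definition to events whose day or month is missing. Instead it uses a shorter limit, so the same event can be classified differently according to how completely its date was written down. The ordering is also illogical: an event with no start date is kept, while one with a known month can be dropped.

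At stake are the treatment-emergent bone and renal AE tables and the SAE tables. The study exists to describe bone and renal safety, and the shorter limit can only remove events that the 30-day definition might count. With 15 subjects per group, one subject moves a group percentage by 1/15 = 6.7 points.

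**Working it through.** The plan states no figure to reproduce, so the check is a comparison of calendar dates.

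**Inputs.** The limits are last dose + 30 days (SAP 7.1.5.1) and the month or year of last dose + 7 days (SAP 7.1.5.2). SAP 2.1 puts the first patient's first visit in July 2015 and the last patient's last visit in April 2018. I took last-dose dates from 1 July 2015 to 30 April 2018: 184 + 366 + 365 + 120 = 1035 dates. The day limits are my assumption, as is a uniform spread of last-dose dates and onset days.

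**Example with a loss.** Last dose is 20 March 2018, so day 7 is 27 March and day 30 is 19 April. An AE dated 10 April 2018 is treatment-emergent. The same AE recorded only as April 2018 is not, because April is later than the month of day 7.

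**Examples without a loss.** With last dose on 1 March 2018, both limits (8 and 31 March) fall in March. With last dose on 28 March 2018, both (4 and 27 April) fall in April.

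**How often the limits differ.** The limits are 23 days apart, so a month boundary should fall between them for roughly 23/30.4 of dates. Enumeration gives:

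- different months: 782/1035 = 75.6%
- different years: 69/1035 = 6.7% (three year-ends × 23 days)

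**Share of in-window onsets excluded, given that the date is partial.**

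| True onset after last dose | Month and year recorded | Year only recorded |
|---|---|---|
| Days 1–7 | 0% | 0% |
| Days 8–30 | 39.4% | 3.5% |
| Days 1–30 | 30.2% | 2.7% |

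The first and last rows agree with the middle one: 39.4% × 23/30 = 30.2%. About 61% of month-only onsets on days 8 to 30 are still counted. An onset on or before last dose is never excluded by the upper limit.

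**With the 30th day instead.** No onset on days 1 to 30 is excluded. Of true onsets on days 31 to 60 recorded by month only, 49.1% would be counted, against 2.7% now.

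**Rough number of events.** Protocol 8.9 expects 4–5 renal or bone adverse drug reactions per 100 subjects over 96 weeks (672 days). Take 5, a constant rate, and a 30-day period after last dose for each of the 30 subjects:

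- events in the window: 5/(100 × 672) × 30 × 30 = 0.067
- excluded if every date were month-only: 0.067 × 0.302 = 0.02

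This covers drug reactions only. All bone and renal AEs plus all SAEs could be several times more, but most dates should be complete.

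**The case against.** The case for leaving the rule alone is mainly that it hardly matters, and much of that stands.

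- **Scope.** A reader might infer that every treatment-emergent table is undercounted. The documents do not support that. Laboratory abnormalities have their own 30-day rule (SAP 7.2.2), deaths are summarised without a treatment-emergent restriction (7.1.6), and the BMD endpoints (7.3) do not use onset dates. AEs leading to discontinuation, dose change or interruption would ordinarily begin by last dose.
- **Size.** A reader might take 75.6% or 30% as the share of events lost. These are calendar shares. They apply only to an event that starts after last dose and has a partial date, and the documents give no frequency for such events.
- **Early stopping.** It is tempting to add that 28 of 30 subjects stopped before Week 96 (SAP 2.1 reports two completers). That adds little: completers also have a last dose followed by the same 30 days.
- **Certainty.** Not every exclusion is wrong, since a later-month date may hide an onset after day 30. SAEs are collected through post-treatment follow-up (Protocol 7.3), which can last 24 weeks, so such events can exist.
- **Visibility.** SAP 7.1.6 lists all AEs with a treatment-emergent flag. With 30 subjects and a descriptive analysis, a reader could find the case.
- **Protocol.** Protocol 8.6.2 also says that events "after the last dose of Tenofovir DF will be included in data listings", and 8.6 summarises data only to last dose. That is a separate inconsistency. It gives no support for 7 days, and SAP 7.1.5.1 settles the AE window at 30.

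None of this explains why the two subsections differ. At the lower end, 7.1.5.2 already counts any event in the month of first dose, although it may precede that dose. Counting an event that could lie inside the window is thus the SAP's own approach at the lower limit and for undated events. Only the upper limit departs from it.

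**Conclusion.** The inconsistency is real and worth correcting, but its effect is probably very small. The two subsections set different upper limits for one classification. The error can run in one direction only: an AE or SAE that may lie inside the 30-day window is left out of the treatment-emergent tables, though it remains listed. Under uniform dates, 30.2% of month-only onsets on days 1 to 30 would be excluded, and 2.7% of year-only onsets. The number of events actually affected cannot be derived from the documents; the rough calculation puts it well below one. BMD results are untouched.

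**What to change.** In SAP 7.1.5.2, second criterion, replace the 7th day with the 30th day, so that the limit matches 7.1.5.1. If 7 days was intended, state the reason.

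The cost is one word in the SAP and one constant in the program, with no new data. The trade-off is that some month-only events with true onset after day 30 would be counted: about 49% of those on days 31 to 60, if recorded at all, against about 3% now. Routine collection of bone and renal AEs ends at day 30, so this would mainly concern SAEs. It is the conservative direction for a safety summary.
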